Cover Page

Title: A Prospective Study of Evaluation of Operative Duration as a Predictor of Mortality in Pediatric Emergency Surgery: Concept of 100 Minutes Laparotomy in Resource-limited Setting

NCT Identifier Number: Not assigned

Document Date: 31/03/2017

Aims & Objectives

The primary objectives of our study were to quantify the effect of duration of emergency laparotomy in children on mortality and to identify a rough cut-off duration of laparotomy to serve as a guide so that such a laparotomy can be planned to optimize pediatric surgical patient outcome in terms of decreased mortality.

The secondary objectives included identifying factors that increase the time of emergency laparotomy and identifying measures that could be applied to reduce the time of laparotomy significantly and improve outcome.

Materials & Methods

This is a prospective study which was conducted at a government teaching institution over a period of 24 months. Ethical approval was provided by the Ethical Committee of the University and was conducted in accordance with guidelines of Good Clinical Practice and the Declaration of Helsinki. Written informed consent was taken from all patients.

All pediatric patients in the age group of 5 to 10 years presenting with acute abdomen diagnosed clinically and radiologically to be having a diagnosis of secondary peritonitis and obstruction; who were adequately resuscitated (with a minimum resuscitation period of at least 1 hour) pre-operatively and underwent definitive surgery by a single surgeon (pediatric surgery senior resident) in the emergency were included in the study. Also, only those patients who had a PRISM-III (Pediatric Risk of Mortality III) score (Figure 1) of ≤ 8 at presentation were included to avoid the confounding effect of pre-operative variables that might affect mortality. All patients were adequately resuscitated in terms of temperature, central nervous system (Glasgow Coma Scale, pupillary reflexes), cardiovascular system (systolic blood pressure, heart rate) and respiratory system (oxygen saturation $> 95\%$, $p\text{CO}_2$, pH, PaO_2) parameters so that they were brought within 0 score range of PRISM-III score at the end of resuscitation and before shifting to the operation theatre. Furthermore for inclusion only those pediatric patients were considered who presented within 72 hours of initial onset of symptoms, operated within 24 hours of initial presentation and who died in index hospital admission within 30 days.

Patients who underwent damage control surgery, whose PRISM – III score was >9 at any point of time before undergoing laparotomy or inability to achieve adequate resuscitation (PRISM-III score >0 before shifting to operation theatre) and/or requirement of resuscitation beyond 4 hours of presentation were excluded from the study.

All the patients were shifted to pediatric intensive care unit (PICU) after the operation where dedicated staff and pediatrician were available for monitoring of patient.

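### Does the plan need changing because the title names 100 minutes while a primary objective is still to find the cut-off?

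*Protocol*

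**What the plan says.** The figure of 100 minutes appears once, in the title on the Cover Page: "Concept of 100 Minutes Laparotomy in Resource-limited Setting". No source or rationale is attached to it, and it does not return in the objectives or methods.

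Aims & Objectives gives two primary objectives. The first is "to quantify the effect of duration of emergency laparotomy in children on mortality". The second is "to identify a rough cut-off duration of laparotomy to serve as a guide", with no value stated.

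Materials & Methods describes one cohort, "conducted at a government teaching institution over a period of 24 months", of children who "underwent definitive surgery by a single surgeon". No further data set is mentioned. The document states no sample size, expected number of deaths, significance level, rule for choosing a cut-off or test at the cut-off. Aims and methods are written in the past tense.

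**The concern.** The title supplies a number that the objective says has yet to be found. Two readings are open. In one, 100 minutes is a prior hypothesis that the study evaluates. In the other, it is the value that looked best in these children and was then carried into the title.

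The readings support different claims. A threshold set in advance can be tested at its nominal level. A threshold searched for and judged in the same children looks better than it is: its sensitivity and specificity are optimistic, and an unadjusted p-value at the selected cut is too small. Because the cut-off is meant to guide the planning of emergency laparotomies, a fitted value presented as a tested one would appear sharper and more certain than the data allow. With one cohort and no second data set described, nothing in the document guards against this under the second reading.

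**Working it through.** **1. No figure to reproduce.** The Protocol gives no sample size, event rate, power or effect size, so there is no calculation of its own to check. The question is first one of reading.

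**2. The texts side by side.**

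- Title: names 100 minutes and calls it a concept.
- Second primary objective: a rough cut-off, to be identified, as a guide.
- First primary objective: the effect of duration on mortality, which needs no cut-off and can be answered with duration as a continuous variable.
- Methods: one institution, 24 months, a single surgeon. The single surgeon bears on generalisability and says nothing about where 100 came from.
- Tense: the past tense fits a value derived from the data but does not establish it.

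Title and objective are unreconciled, but they do not exclude each other, since a study can start from a working value and refine it.

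**3. How much the distinction could matter.** All inputs here are assumptions. Durations are normal with mean 100 and SD 30 minutes, duration has no true effect, and there are 4000 simulated studies per setting. For a split into groups of size n1 and n2 with death proportions p1 and p2 and overall proportion p,

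z = |p1 − p2| / √[p(1 − p)(1/n1 + 1/n2)], called significant if z > 1.96.

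This was applied once at a fixed 100 minutes, and once at the largest z over all splits between the 10th and 90th percentiles.

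| Children | Mortality | Fixed 100 min | Best split in same data |
|---|---|---|---|
| 100 | 10% | 4.9% | 38.2% |
| 100 | 20% | 5.2% | 40.1% |
| 100 | 30% | 4.9% | 41.0% |
| 200 | 10% | 5.2% | 39.8% |
| 200 | 20% | 4.9% | 42.1% |
| 200 | 30% | 5.4% | 44.0% |
| 400 | 10% | 5.2% | 44.9% |
| 400 | 20% | 5.0% | 45.1% |
| 400 | 30% | 5.7% | 46.1% |

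The simulation error is small: √(0.05 × 0.95 / 4000) = 0.3 percentage points near 5%, and √(0.4 × 0.6 / 4000) = 0.8 points near 40%.

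**4. Dependence on the selection rule.** A second set of simulations used log-normal durations (median 100 minutes, SD of log 0.3), 100 or 200 children and 10% or 20% mortality. With no true effect, the false-positive rate was 29% to 43% when the cut with the smallest p-value was taken, and 13% to 20% when the cut with the largest Youden index was taken. With an odds ratio of 1.5 per SD of log duration, the apparent Youden index averaged 0.22 to 0.32 against a true value of about 0.14 at the selected cut. The optimism is therefore 0.22 − 0.14 = 0.08 to 0.32 − 0.14 = 0.18. The middle 80% of selected cuts ran from 82 to 134 minutes (100 children, 10% mortality) and from 87 to 125 minutes (200 children, 20% mortality).

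**5. What these numbers can decide.** They show how optimal cut-offs behave in general. They cannot show whether 100 minutes was prior or derived. The selected cuts lie around 100 minutes because the durations were centred there by assumption. The null rates run from 13% to 46% according to the rule and the inputs assumed, and the Protocol commits to no rule. The simulations also assume a cohort with survivors. The inclusion text, read literally, restricts the cohort to children who died; that is a separate matter.

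**6. What a change would consist of.**

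- A sentence on the origin of 100 minutes: this records a fact and alters no procedure.
- Duration as a continuous variable for the first objective: the wording already allows it, and nothing in the document proposes dichotomising.
- A bootstrap interval for the cut-off, optimism-corrected performance and no unadjusted p-value: sound practice if the cut-off is derived here, but ordinary content of an analysis plan.

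**The case for a change.** The strongest argument for a change is that this is more than a missing analysis detail. Whether a study tests a threshold or derives one belongs to its objectives, and the Protocol states those. The ambiguity concerns a primary objective, the result is intended for practice, only one cohort is available, and one sentence would settle the matter. In every setting tried, selecting and judging the cut in the same data inflated its apparent performance.

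Part of this stands. The status of 100 minutes is unclear, and a reader would be better served by knowing its source. If the value was fitted, it should be described as exploratory. What does not stand is the step from unclear to wrong. The inflation occurs only if 100 minutes was searched for in these data and then presented without allowance, and the text establishes neither. If it was set beforehand, the difficulty disappears. The objective also qualifies itself, since it asks for a rough value to serve as a guide and claims no precise or validated threshold.

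**Conclusion.** The ambiguity is real and minor, and no change to the plan follows. Title and objective can be read together without contradiction, and the document makes no choice of cut-off method that could be called faulty. An analyst who derives a threshold from a single cohort would be expected to report its uncertainty and call it exploratory; the place to say so is an analysis plan, which may exist but is not shown.

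The possible size of the problem (a false-positive rate of 13% to 46% instead of about 5%, or a Youden index overstated by 0.08 to 0.18) is conditional on two things. One is that 100 minutes was fitted to these children and reported uncorrected. The other is the assumed numbers, mortality, spread of durations, effect size and selection rule, none of which the Protocol gives. Stating where 100 minutes comes from would be a courtesy to the reader and would leave the design and the analysis as they are.

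### As written, death is a condition for inclusion, so the cohort contains no survivors and neither primary objective can be met

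*Protocol*

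**What the plan says.** Aims & Objectives gives two primary objectives. The first is "to quantify the effect of duration of emergency laparotomy in children on mortality". The second, stated in the same sentence, is "to identify a rough cut-off duration of laparotomy to serve as a guide". Materials & Methods describes the design: "This is a prospective study which was conducted at a government teaching institution over a period of 24 months". It adds: "Written informed consent was taken from all patients".

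The eligibility text in Materials & Methods starts broadly, with "All pediatric patients in the age group of 5 to 10 years presenting with acute abdomen", and adds diagnostic, resuscitation, surgical and PRISM-III conditions. A further restrictive sentence follows. It begins "Furthermore for inclusion only those pediatric patients were considered who presented within 72 hours of initial onset of symptoms" and ends "operated within 24 hours of initial presentation and who died in index hospital admission within 30 days".

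The exclusions cover damage control surgery, PRISM-III limits and resuscitation; the last reads "requirement of resuscitation beyond 4 hours of presentation were excluded from the study". None of them concerns survival.

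**The concern.** The restrictive sentence joins three conditions with a single conjunction: time from symptom onset to presentation, time from presentation to operation, and death. The first two are known by the time of surgery. The third is the outcome under study. Selecting on the outcome removes the comparison group that both primary objectives need, because an effect on mortality and a discriminating cut-off each require survivors as well as deaths.

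The clause also sits badly with a prospective design and consent from every patient. A death up to 30 days later cannot be known when a child is enrolled.

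The sentence decides who is in the cohort for the main question. A reader who takes it at face value must conclude that the study cannot answer that question. A reader who takes it charitably must assume that the written criteria do not describe the children who were analysed.

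**Working it through.** The protocol states no sample size, event rate or power, so there is no figure of its own to reproduce. The core of the check is logical.

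**Step 1. Apply the rule as written.** Let T be operative duration and D = 1 for in-hospital death within the 30-day window. Inclusion requires D = 1, so P(D = 1 | included, T = t) = 1 for every t.

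**Step 2. Consequences for the objectives.** For any cut-off c, including the title's 100 minutes:

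- Risk difference = 1 − 1 = 0, and risk ratio = 1/1 = 1, whatever the true effect.
- Odds ratio = (deaths long × survivors short) / (survivors long × deaths short). Both survivor counts are 0, so this is 0/0.
- Sensitivity can be computed. Specificity = survivors at or below c / all survivors = 0/0, so there is no ROC curve and no AUC.
- With every D = 1, the logistic log-likelihood is −Σ log(1 + exp(−(a + b·tᵢ))). For any slope b it approaches its upper limit of 0 as the intercept a grows, so the data do not distinguish one slope from another.

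**Step 3. Illustration.** The inputs are assumptions, since the protocol gives none: 100 children on each side of 100 minutes, with death risk 10% (short) and 30% (long).

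| | Long: died / alive | Short: died / alive | Odds ratio | Risk difference | Specificity |
|---|---|---|---|---|---|
| All operated children | 30 / 70 | 10 / 90 | (30×90)/(70×10) = 3.86 | 30% − 10% = 20 points | 90/160 = 0.56 |
| Literal rule | 30 / 0 | 10 / 0 | 0/0 | 100% − 100% = 0 | 0/0 |

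The literal rule keeps 30 + 10 = 40 children and drops 70 + 90 = 160 of 200 (80%).

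**Step 4. Range of assumed risks, 100 per side.**

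| Risk short vs long | Odds ratio, all children | Dropped by literal rule | Odds ratio, literal rule |
|---|---|---|---|
| 5% vs 10% | (10×95)/(90×5) = 2.11 | 185/200 = 92.5% | undefined |
| 5% vs 20% | (20×95)/(80×5) = 4.75 | 175/200 = 87.5% | undefined |
| 10% vs 30% | 3.86 | 160/200 = 80% | undefined |
| 20% vs 40% | (40×80)/(60×20) = 2.67 | 140/200 = 70% | undefined |

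The assumed risks change only the share of children lost. The failure in Step 2 is the same for all of them.

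**Step 5. Look for correcting text.** No sentence says that survivors are included, and none defines mortality separately. The death clause is the only place where a setting and a time window for death appear.

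**Step 6. Try a narrower reading.** Suppose the clause means that, among deaths, only those in hospital within 30 days count, and children who died later or after discharge are removed. Inclusion would still depend on the outcome.

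**The case against.** The strongest reply is that this is a drafting slip. The title treats duration as a predictor of mortality, both objectives presuppose survivors, the eligibility text opens with all children in the age range, and no exclusion concerns survival. On that reading the clause is an outcome definition in the wrong place, and no estimate is affected. This is the likelier explanation, and it stands as one. It does not remove the fault: the reader has to infer it against the plain wording, and nothing in the protocol confirms it.

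A second reply is that inclusion may mean the analysed cohort, settled afterwards. The protocol does use the word for matters not known at presentation, such as the type of operation performed. This weakens the argument that the rule cannot be applied at enrolment. It does not touch the conflict with the objectives, because a cohort settled afterwards by death is still selected on the outcome.

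A third reply is that endpoint detail may be in a statistical analysis plan that is not shown. That is fair for the time origin, which is minor here, and the absence of a separate endpoint definition should not by itself add weight. It does not answer the main point, which is an eligibility rule that the protocol states, and states wrongly.

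Finally, the study is described in the past tense. If only deaths really were included, deleting the clause would misdescribe the cohort. That stands, and the correction has to begin with a statement of who was included.

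**Conclusion.** The concern holds as stated and must be fixed. Under the written rule mortality is 100% at every duration, and neither primary objective can be met. This follows from the wording alone and rests on no assumed rate; the 70% to 92.5% of children dropped in the illustration does depend on the assumed risks. If survivors were enrolled, which is probable, the numerical effect is nil and the defect is confined to the text. The protocol does not show which reading was applied.

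**What to change.** 1. State who was included, and whether operative durations were recorded for survivors. The protocol does not describe data collection, so this cannot be taken for granted.
2. If survivors were enrolled, remove the death clause from the inclusion criteria. State that all children who meet the pre-operative and operative criteria are included and analysed whatever their outcome.
3. Restate the same event as the mortality endpoint, keeping the protocol's setting and 30-day window, and name the time origin (presentation or operation). Under the protocol's own 24-hour limit from presentation to surgery, the two origins differ by at most 1 day.
4. If only deaths were included, the primary objectives cannot be met from this cohort and must be restated.

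If survivors were enrolled, the cost is one clause moved and one sentence added, with no change of endpoint and no extra follow-up. If only deaths were included, the cost is larger, because the study's purpose itself has to be rewritten.

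### Death is written as a condition for inclusion, so followed literally the study has no survivors; if the clause is meant as the outcome, deaths after discharge but before day 30 go uncounted

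*Protocol*

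**What the plan says.** Aims & Objectives gives two primary objectives. The first is "to quantify the effect of duration of emergency laparotomy in children on mortality". The second, meant to help in planning such operations, is "to identify a rough cut-off duration of laparotomy to serve as a guide". Both need children who died and children who survived, across the range of durations.

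The only wording that says which deaths matter is in the eligibility paragraph of Materials & Methods. Its last sentence opens "Furthermore for inclusion only those pediatric patients were considered who presented within 72 hours of initial onset of symptoms", adds a limit on the time from presentation to operation, and ends with the condition "who died in index hospital admission within 30 days". Grammatically, death is one of the inclusion criteria.

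The protocol has no separate definition of the mortality outcome. The only post-operative observation it describes is that "All the patients were shifted to pediatric intensive care unit (PICU) after the operation", where they were monitored. No contact after discharge is mentioned. No mortality rate, length of stay or number of deaths is given.

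**The concern.** Two problems sit in the same clause.

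**Selection on the outcome.** If death is required for inclusion, the data hold no survivors. A study of how duration relates to mortality then has nothing to compare.

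**Outcome ascertainment.** If the clause is instead meant to define the outcome, it restricts both place (index admission) and time (30 days). Observation of each child then ends at discharge or day 30, whichever comes first. A child discharged on day 7 who dies at home on day 15 is not a counted death. Length of observation therefore varies between children and could vary with operative duration, which is the exposure. If so, part of an observed duration–mortality gradient, and part of any cut-off drawn from it, could reflect where children died and not whether they died. Adjusting for covariates cannot recover deaths that were never recorded.

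**Working it through.** The protocol states no sample size, event count or mortality rate, so there is no figure to reproduce. All rates below are assumptions.

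**Literal reading.** Let n be the children included in a duration band and d those who died. If death is required for entry, d = n in every band.
- Mortality = d/n = 100% at every duration.
- Risk ratio, long versus short = 100%/100% = 1, whatever the truth.
- Odds = d/(n − d) = n/0, so the odds ratio is undefined.
- Specificity of any cut-off has the number of survivors, 0, as its denominator, so an ROC-type cut-off cannot be found.

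**Outcome reading.** Let p be true 30-day mortality and m the share of those deaths that occur after discharge and are missed. Observed mortality = p × (1 − m). The observed risk ratio is

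RR = [p_long × (1 − m_long)] / [p_short × (1 − m_short)].

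The true RR is multiplied by (1 − m_long)/(1 − m_short), so it is unchanged exactly when the two shares are equal.

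| Missed share, short / long | Observed mortality if truth is 5% / 15% | RR (true 3.00) | RR if truth is 10% / 10% (true 1.00) |
|---|---|---|---|
| 10% / 10% | 4.50% / 13.50% | 3.00 | 1.00 |
| 10% / 2% | 4.50% / 14.70% | 3.27 | 1.09 |
| 20% / 5% | 4.00% / 14.25% | 3.56 | 1.19 |
| 30% / 10% | 3.50% / 13.50% | 3.86 | 1.29 |
| 5% / 20% | 4.75% / 12.00% | 2.53 | 0.84 |

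For example, in the third row: 0.15 × 0.95 = 0.1425, 0.05 × 0.80 = 0.0400, and 0.1425/0.0400 = 3.56. On the odds-ratio scale, equal shares of 10% move the true value of 3.35 only to 3.31.

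The larger distortions need a fair number of deaths at home. Missing 30% of deaths at 5% mortality means 0.30 × 5% = 1.5% of all children with short operations die between discharge and day 30. Nothing in the protocol supports or excludes that.

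**Start of the 30 days.** The clause does not say whether the window runs from presentation or from operation. Eligibility requires operation within 24 hours of presentation, so the two differ by at most one day. This hardly matters, but the start should be stated.

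**The case against.** The clause is most naturally a misplaced outcome definition. The study is described as prospective, and death cannot be known when a child enters, so the literal rule could hardly have been applied at enrolment. A reader might infer that only children who died were studied. The protocol does not show that; it shows a rule which, as written, would produce it. The objection explains how the sentence may have arisen but leaves the sentence wrong. A SAP, if one exists, might define the outcome, but a separate outcome definition would not remove death from the inclusion criteria.

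On the outcome reading, in-hospital mortality is a common endpoint, and in a resource-limited setting follow-up after discharge may itself be incomplete. That is fair, and is why the fix allows an in-hospital endpoint if it is declared as such.

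A stronger claim is tempting: that short operations lead to early discharge, so their deaths are missed more often and the effect of duration is exaggerated. The protocol does not support it. It gives no discharge timing or post-discharge deaths by duration. Earlier discharge alone is also not enough, because children sent home early after simple operations may be those least likely to die at home. The direction is open.

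Finally, the text is in the past tense. If the study is complete, day-30 contact may no longer be possible. That limits the remedy for follow-up but not the correction of the eligibility wording.

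**Conclusion.** The concern holds in two parts of unequal certainty.

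The first needs no assumption. As written, death is an inclusion condition, and under that rule neither primary objective can be met.

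The second is conditional. If the clause is the outcome definition, deaths between discharge and day 30 are lost, and this can bias the duration–mortality relation and the cut-off when the missed share differs by operative duration. Neither size nor direction can be determined from the protocol. There is no bias in the risk ratio with equal shares, inflation if more deaths are missed after short operations, and attenuation if more are missed after long ones. The range shown (2.53 to 3.86 around a true 3.00, and 0.84 to 1.29 around a true 1.00) rests wholly on assumed mortality and missed shares. It illustrates sensitivity and does not estimate the error in this study.

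**What to change.** 1. Remove death from the eligibility criteria. Include every eligible child operated on, survivors and deaths alike.
2. Define the outcome in its own sentence: death from any cause within 30 days of the operation, in or out of hospital.
3. Obtain day-30 vital status by telephone or routine visit for children discharged earlier, where obtainable.
4. Report index-admission death alongside, with the number of children whose day-30 status is unknown.
5. If only in-hospital death can be observed, state that as the endpoint and report length of stay by operative duration, so that readers can judge whether observation differed with the exposure.

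Items 1 and 2 are wording changes. Item 3 costs one contact per child discharged before day 30. The downside is some loss to follow-up in a resource-limited setting, which item 4 makes visible. If the study has closed and contact is no longer feasible, items 1, 4 and 5 still apply.

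### Does excluding damage control surgery by the operation received undermine the duration–mortality result or the cut-off?

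*Protocol*

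**What the plan says.** Under Materials & Methods, the protocol includes children who "underwent definitive surgery by a single surgeon (pediatric surgery senior resident) in the emergency were included in the study". The exclusion paragraph of the same section begins "Patients who underwent damage control surgery". Both conditions are worded by the operation the child received. Neither says when the choice between the two kinds of operation was made, and no reason is given for this exclusion.

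The severity exclusion in the same sentence does carry a time: it applies where the PRISM-III "score was >9 at any point of time before undergoing laparotomy". The section also describes the result required of resuscitation: "they were brought within 0 score range of PRISM-III score at the end of resuscitation and before shifting to the operation theatre".

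Under Aims & Objectives, the first primary aim is worded as "quantify the effect of duration of emergency laparotomy in children on mortality". The second concerns a threshold for planning, and its wording is "identify a rough cut-off duration of laparotomy to serve as a guide so that such a laparotomy can be planned". A secondary aim is "identifying measures that could be applied to reduce the time of laparotomy significantly and improve outcome". None of these is worded as applying to definitive operations only.

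**The concern.** Age, PRISM-III score and time since onset are known before incision, so a surgeon planning an operation can tell whether a child resembles the cohort. Whether the operation will end as definitive may not be known then. Every eligible child reaches theatre with a PRISM-III score of 0, so one can imagine that some damage control decisions were made during the operation. Eligibility would then depend on an event that follows the start of the exposure and is plausibly related to both its length and to death.

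If so, mortality in short operations would describe only those finished as definitive, and could understate the risk for all children taken to laparotomy. A cut-off resting on that comparison would carry the same limit. The aim of shortening operations would also be pursued in a cohort with no outcomes for damage control operations.

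**Working it through.** **1. What the document supplies.** It gives no count of damage control cases, no mortality by type or length of operation, and no sample size or effect size. There is no figure to reproduce; every number below rests on assumption.

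**2. The two sections side by side.** The objectives name emergency laparotomy in children; the cohort is definitive operations. That difference is real. The objectives equally omit age 5 to 10 years, the peritonitis or obstruction diagnosis, the single surgeon, presentation within 72 hours and successful resuscitation. The eligibility section supplies all of these, and supplies definitive surgery in the same way.

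**3. Timing.** If damage control was chosen before incision, the exclusion is an ordinary restriction. Only a choice made after incision selects on the course of the operation. A missing time does not show which occurred. The score of 0 before theatre could mean that the remaining decisions were mostly intra-operative, or that there were hardly any.

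**4. Effect on short-operation mortality.** Let *f* be the damage control share of all operations, *s* the share of definitive operations lasting at most 100 minutes, *m* damage control mortality, and *q* the probability that a damage control operation lasts at most 100 minutes. Assume 10% mortality in short definitive operations and damage control durations of mean 60, SD 15 minutes. Then *q* = Φ((100 − 60)/15) = 0.996, and

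mortality = [*s*(1 − *f*)(0.10) + *f q m*] / [*s*(1 − *f*) + *f q*].

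For *f* = 5%, *s* = 0.5, *m* = 0.3: (0.0475 + 0.0149)/(0.475 + 0.0498) = 11.9%.

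| Damage control share | Range over *s* = 0.5–0.8, *m* = 0.3–0.5 |
|---|---|
| 1% | 10.2–10.8% |
| 3% | 10.7–12.3% |
| 5% | 11.2–13.8% |
| 10% | 12.4–17.2% |

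With *m* = 0.10 the result is 10.0% throughout.

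**5. Effect on a long-versus-short odds ratio.** Assume 20% mortality in long operations and all damage control cases in the short group.

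- Short definitive mortality 5%, damage control excluded: (0.20/0.80)/(0.05/0.95) = 4.75. Adding cases that make up 2% to 20% of short operations, with 20% to 60% mortality, gives 4.47 down to 1.31.
- Short definitive mortality 10%: 2.25 when excluded, 2.20 down to 1.00 when added.

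The lowest values need damage control to be 20% of short operations with 60% mortality: 0.8 × 0.05 + 0.2 × 0.60 = 16%, and 0.25/(0.16/0.84) = 1.31. Nothing in the document supports those inputs.

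**6. Which analysis is more distorted?** A simulation assumed 25% of children severe at operation (mortality odds ratio 4), damage control only in severe children and likelier with longer intended duration, and a true odds ratio of 1.5 for more than 100 against at most 100 minutes.

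| Severity's effect on duration | No damage control | 5% share, definitive only | 5% share, all operated |
|---|---|---|---|
| none | 1.46 | 1.36 | 1.21 |
| +20 minutes | 2.00 | 1.87 | 1.59 |

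These are crude odds ratios. The all-operated value moves further from the no-damage-control value in both rows (0.25 against 0.10; 0.41 against 0.13). In the second row it ends nearer 1.5, but only because confounding upwards and shortened operations downwards offset each other. Adjusted for severity, both cohorts give 1.49–1.51, which is partly built in because selection depends only on that severity and on duration.

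With a further, unrecorded severity component, the adjusted value is 1.45 without damage control. As the share rises from 1% to 9.5%, it goes from 1.44 to 1.40 in definitive operations and from 1.41 to 1.22 in all operated children.

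Short-operation mortality was lower in the definitive-only cohort in all 32 scenarios with damage control, by 0.2 to 3.9 points. That follows from making damage control both short and confined to severe children; it says nothing about this study.

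**The case for a change.** The strongest argument for acting is that the mismatch in scope needs no assumption: the objectives are wider than the cohort, and membership turns on the operation performed. A reader using the cut-off to plan might apply it to a child whose operation does not end as definitive. Step 5 shows that the excluded cases could matter little or a great deal, and only their number would tell. Restating the objective costs nothing.

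The factual part stands. The bias does not, because it needs a decision time the protocol does not give. Objectives are read together with eligibility criteria, and the cut-off is described as rough and as a guide. The aim of reducing operating time speaks of measures and does not mention abbreviated operations, so the absence of damage control outcomes does not contradict it. Counting exclusions and adding sensitivity analyses are commonly left to an analysis plan or the report; the protocol is silent on them, and silence does not show that the cases went uncounted.

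**Conclusion.** No change to the plan is needed. The restriction to definitive surgery is explicit, and it is a fair trade-off: taking in damage control cases would bring in operations cut short because the child was deteriorating, which mixes reverse causation into the duration effect. Neither the direction nor the size of any bias in the duration–mortality odds ratio can be established from the document. The illustrations run from no effect to a large one, depending wholly on an assumed share, mortality and timing of damage control; at shares of 1–3% the assumed 10% short-operation mortality becomes 10.2–12.3%.

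A sensible report would describe the result as applying to definitive laparotomy and give the number of damage control exclusions, with the time of decision where known. An analysis of all operated children is not required. All of this presumes a cohort containing both deaths and survivors; the inclusion wording about death within 30 days raises a separate question that does not alter this conclusion.
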